7.13 Withdrawal

A patient should be withdrawn from the trial at any time if:

- Patient/legal guardian withdraw consent

If the patient withdraws from the trial, the patient should be asked to attend an EOT visit as soon as possible. Furthermore, if possible the patient should be followed for safety for 6 weeks after last dose of naxitamab for safety reasons.

8 TREATMENTS

8.1 Investigational Medicinal Products (IMPs)

For this trial, Y-mAbs will provide naxitamab, GM-CSF, irinotecan and temozolomide. All 4 products are classified as IMPs. The IMPs provided must be used solely for this trial as described in this protocol and for no other purpose. For further information on naxitamab, GM-CSF and IT refer to the IB and current summary of product characteristics (SmPCs). A summary of the IMPs is provided in [Table 3](#).

No other medicinal products or auxiliary supplies will be provided by Y-mAbs.

Table 3 IMPs provided by Y-mAbs

IMP:	Irinotecan	Temozolomide	Sargramostim (GM-CSF)	Naxitamab
Route:	IV infusion	Orally	Sc	IV infusion
Dosing instruction:	Days 1-5 50 mg/m ² /day	Days 1-5 100 mg/m ² /day	Days 6-10 ¹ 250 µg/m ² /day ¹	Days 2, 4, 8 and 10 ¹ 2.25 mg/kg/day ¹
Pharmaceutical form:	Solution for infusion	Capsules	Lyophilized 250 µg single use vial	Solution for infusion
Unit strength	20 mg/mL	5, 20 and 100 mg	250 µg/vial	4 mg/mL

¹ Please refer to [Appendix 2](#) for dosing days and dose for treatment of patients who discontinue IT treatment

8.1.1 Administration of IMP for Each Patient

The patient must have a well-functioning intravenous catheter before initiating any treatments for IV administration; a central line is recommended. For naxitamab treatment, site should have emergency equipment readily available, and the patient should have 2 well-functioning IV accesses before any naxitamab treatment is initiated.

Please refer to the IMP manual for more details on preparation and administration of temozolomide, irinotecan, GM-CSF and naxitamab.

Before administration of IMPs, patients must meet hematologic, renal and hepatic eligibility criteria for trial entry at the start of each treatment cycle (see Section [7.11.2](#)).

8.1.2 Treatment schedule

Please refer to [Appendix 2](#) if the patient has discontinued IT treatment due to toxicity.

Table 4 Treatment schedule

Treatment days in cycles of 21 days	-3 to 0	1	2	3	4	5	6	7	8	9	10	11-12	13-21
Premedication (8.4.1, 8.4.3)	X	X	X	X	X	X	X	X	X	X	X	X	
Irinotecan 50 mg /m ² /day (IV) + temozolamide 100 mg/m ² /day (orally) (8.1.2.1, 8.1.2.2)		X	X	X	X	X							
Naxitamab 2.25 mg/kg/day IV (9mg/kg/cycle) ¹ (8.1.2.3) ¹			X		X				X		X		
GM-CSF 250 ug/m ² /day s.c (8.1.2.4) ¹							X	X	X	X	X		

1) Patients achieving a CR or PR should receive 8 naxitamab cycles or 5 additional naxitamab cycles following the OR, whichever provides the longest treatment with naxitamab. Patients who have achieved a MR or SD at completion of the 8 cycles may receive naxitamab + GM-CSF consolidation treatment for 5 cycles administered at every 6 weeks

8.1.2.1 Temozolomide

Temozolomide will be administered orally at 100 mg/m²/day on Days 1-5. For patients, whose body surface area (BSA) is $\geq 0.5\text{m}^2$, the temozolomide dose should be rounded off to the nearest 5 mg (Appendix 3). Administration should preferable be on an empty stomach (at least 1 hour before or 2 hours after food intake) to decrease nausea and vomiting and improve absorption. For patients who are unable to swallow capsules, the capsule content may be mixed with apple sauce or apple juice or be prepared for suspension, please refer to Appendix 6 and Appendix 7. If emesis occurs within 20 min of taking a dose of temozolomide, the dose may be repeated once. If emesis occurs after 20 min, the dose should not be repeated.

8.1.2.2 Irinotecan

Irinotecan will be infused IV at 50 mg/m²/day over 90 min on Days 1-5. Antiemetics should be administered as necessary according to local SoC. Irinotecan should be administered at least 1 hour after temozolomide has been given.

8.1.2.3 Naxitamab

On days when co-administered with GM-CSF, naxitamab infusion is started ≥ 60 min after GM-CSF.

On days when co-administered with IT (i.e., Days 2 and 4), it is recommended to start naxitamab infusion at least 1 hour after irinotecan administration to allow for preparations and administration of pre-medications.

Naxitamab should be infused IV at 2.25 mg/kg/day on Days 2, 4, 8 and 10 for a total dose of 9 mg/kg per cycle (Please refer to Appendix 2 for details on naxitamab treatment if the patient has discontinued IT treatment due to toxicity). Administration of naxitamab should be adjusted according to Section 8.4.5, if selected naxitamab adverse reactions are observed. If any events occur fulfilling a general discontinuation criterion the patient must be withdrawn from all treatments immediately and enter long-term FU, see Section 7.12.

At Cycle 1 Day 2 (C1D2):

Naxitamab should be infused over approximately 60 min.

All subsequent naxitamab infusions:

Naxitamab should be infused over approximately 30 min.

Special circumstances

The infusion may be given over approximately 60 min. at Day 2 of any cycle at the investigator's discretion if:

- The patient during C1D2 experienced naxitamab related hypotension:
 - Grade 4 **or**
 - Grade 3 not adequately responding to intervention
- At the investigator's discretion due to severe infusion related adverse drug reactions not adequately responding to interventions

The 60/30 min infusion time is a minimum infusion time. If infusion pause or infusion rate reduction is required due to infusion related AE (see Section [8.4.5](#)) the infusion time will become longer.

Naxitamab treatment in an out-patient setting is defined as a naxitamab infusion performed in the ambulatory setting.

In-patient treatment (i.e. requiring hospitalization) includes both short term admissions and admissions requiring overnight stay.

8.1.2.4 GM-CSF

GM-CSF will be administered sc at 250 $\mu\text{g}/\text{m}^2/\text{day}$ on Day 6 to Day 10. (Please refer to [Appendix 2](#) for details on GM-CSF treatment if the patient has discontinued IT treatment due to toxicity). The first dose of GM-CSF should be administered at the trial site. GM-CSF and auxiliary supplies will be provided to the patient/parents for administration at home after the patient/parents has received appropriate training on how to administer the drug. Thorough instructions should be given orally and in writing including instructions on how to store and administer the reconstituted GM-CSF at home. The patient/parents will be asked to fill in records of administration (patient diary). Auxiliary supplies include e.g., syringe, needles, sharps disposal container, gloves, alcohol wipes.

GM-CSF must not be administered simultaneously with, within 24 hours preceding or 24 hours following receipt of chemotherapy or radiotherapy.

8.1.3 Treatment delays and missed dosing

Minor adjustment of the treatment schedule due to medical circumstances (e.g., infection) at the discretion of the investigator or non-medical circumstances (e.g., public holidays) is allowed.

It is allowed to postpone the start of a new cycle due to IT toxicity for up to 21 days after the planned subsequent cycle start date (i.e., < 3-weeks delay in start of next cycle) (please see treatment discontinuation criteria Section [7.12](#)).

If a naxitamab dose is missed, administer the missed dose on Day 12. In that case, treatment with GM-CSF at 250 µg/m²/day should be continued until Day 12 (i.e., treatment from Day 6 to Day 12). Please refer to [Appendix 2](#) if the patient has discontinued IT treatment due to toxicity.

8.1.4 Treatment after Discontinuation of IMP

If the patient prematurely discontinues all IMPs and after End of Trial, any treatment deemed safe and justified by the Investigator can be administered according to clinical practice and at the discretion of the Investigator.

8.1.5 Drug Accountability and Compliance Check

Each trial site will be supplied with sufficient IMPs for the trial on an ongoing basis. IMPs will be distributed to the trial sites according to enrollment.

Drug accountability must be documented by the trial staff on the dedicated forms. The investigator or designee is responsible for drug accountability and record maintenance (i.e., receipt, accountability, and final disposition records). The patient/parents will be provided with a diary to record the administration of GM-CSF at home. The patient/parents should bring these records to the hospital visits together with all used, partly used and unused GM-CSF, as instructed by the investigator. All returned, expired, or damaged IMP must be stored separately from non-allocated trial products. Non-allocated IMP including expired or damaged IMP must be accounted as un-used, at the latest at closure of the trial site. For more information on accountability procedures, please refer to IMP manual.

Clinical personnel at the site will record in the source notes the timing (i.e., date and time) and the way of administration of all administrations of irinotecan, temozolomide and naxitamab, including changes to infusion rate and dose reductions. Furthermore, the clinical personnel will assess the GM-CSF treatment compliance by reviewing the patient diaries. Any reasons for non-compliance should be documented in the hospital records and be discussed with the patient/parent(s) as applicable.

8.1.6 Packaging and Labelling

Packaging and labelling of naxitamab, GM-CSF and IT will be outsourced to a clinical packaging contract manufacturing organization. All products are labelled according to Annex 13, EudraLex, volume 4 and local requirements. Each unit of product are uniquely numbered. Further detailed information on labelling and packaging is described in the IMP manual.

8.1.7 Storage and Handling

The IMPs provided by Y-mAbs must be stored according to the IMP label in a secure location with controlled access separately from normal clinical stock. The storage conditions must be monitored for adherence to label claims. Temperature monitoring data must be reviewed by the Clinical Research Associate (CRA) during monitoring visits. Any deviations in storage temperature must be reported immediately and the IMP must not be used until acceptance is received. Monitoring must be done using a calibrated, stationary, and continuously recording system. As a minimum a calibrated min/max thermometer is required. Further detailed information on storage and handling of the IMP is described in the IMP Manual.

8.2 Medication Errors, Misuse and Abuse

Medication errors, misuse and abuse must be reported in the medication error eCRF

Medication errors and uses outside what is foreseen in the protocol, including misuse and abuse of the IMPs may include:

- Administration of wrong drug
- Wrong route of administration, such as intramuscular (IM) instead of IV
- Accidental administration of a lower or higher dose than intended. An overdose is defined as a patient receiving a dose of the IMP exceeding 10% as compared to the protocol-specified dose. An underdose is defined as a patient receiving a dose of the IMP less than 10% as compared to the protocol-specified dose.
- Misuse: Inappropriately use of a medicinal product outside the terms of the protocol
- Abuse: Intentional excessive use of the IMP which is accompanied by harmful physical or psychological effects (*e.g., suicide attempt*)

If a medication error results in an AE, the AE must also be reported in the electronic case report form (eCRF). If the event qualifies as a SAE it must be reported using the paper Clinical AE Report form in addition to the AE form in the eCRF (see also Section 10 for reporting of AEs).

8.3 Technical complaint

A technical complaint is any written or oral communication that states any dissatisfaction regarding the IMP characteristics and alleges a product defect. A technical complaint can be related to *e.g.*, the product appearance (discoloration, presence of particles or sediments), product container (damaged or missing seal), product label (damaged, missing, misleading), or consignment (wrong amount of vials in the package). A complaint should also be initiated if the product is suspected to be falsified.

Complaints should be immediately (within 24 hours) reported to Y-mAbs Quality Assurance.

Please refer to the IMP manual for information regarding reporting of a technical complaint.

8.4 Concomitant Therapy

A concomitant medication is any medication other than the IMPs. All concomitant medications (including over the counter) that the patient is receiving at the time of screening or receives during the trial must be entered in the eCRF with the following information:

- Generic name (preferred) or trade name
- Start date
- Stop date of administration or ongoing at trial termination
- Time of administration if administered as naxitamab pre-medication (see Section 8.4.1)
- Indication/ reason for use

- Dose
- Frequency
- Outcome (for anti-cancer treatments during long-term FU).

Any changes to concomitant during the trial should be recorded in the eCRF. If a change is due to an AE/SAE, then the AE/SAE must be recorded according to Section 10. During long-term FU, only new anti-cancer therapy should be collected.

8.4.1 Pre-medications Prior to Naxitamab Infusions

Pre-medication is needed to mitigate expected AEs with naxitamab. These include pain, infusion-related reactions, hypotension, allergic reactions, nausea/vomiting and potentially anxiety.

Infusion with naxitamab is associated with pain that may be severe. The pain may involve the abdomen, lower back, chest, legs and arms. The duration may vary but, for most patients, the pain lasts for a couple of hours, and tends to be worst during the naxitamab infusion, subsiding approximately 15 min after end of infusion. Due to the pain, patients may “hold their breath”. A marked variation in the naxitamab-associated pain may be observed from infusion to infusion, and hence the recommended opioid dosages below are applicable only to the first infusion. Opioid pre-medications for mitigation of pain during subsequent infusions of naxitamab and pain medications after completion of the naxitamab infusion should be adjusted at the discretion of the investigator.

All medications (including opioid usage) should be captured on the concomitant medication eCRF.

At home

To reduce the risk of pain, gabapentin should be administered from Day -3 to Day 12 of each cycle according to local SoC (e.g., dose of 5 to 10 mg/kg with a max dose of 600 mg).

It is recommended to titrate to the final effective dose during the first 3 days of treatment:

Day -3: Once daily; Day -2: Twice daily; Day -1 and until Day 10: 3 daily doses (please refer to [Appendix 2](#) if the patient has discontinued IT treatment due to toxicity).

After completion of the naxitamab treatment (i.e. Day 10), it is recommended to taper off the gabapentin treatment: Day 11: Twice daily; Day 12: Once daily. If nerve pain lingers, the patient may continue gabapentin on twice daily dosing for up to a week post naxitamab treatment before further weaning.

At hospital

- Saline solution 0.9% (to reduce risk of severe hypotension)
 - Patients should be preloaded with saline 0.9% infusion 10mL/kg over 1 hour just prior to the start of all naxitamab infusions
- Opioids
 - Per os (PO) opioids are preferred over IV to diminish IV related side effect such as hypotension, respiratory depression, and/or decreased responsiveness
 - Oxycodone 0.1 – 0.2 mg/kg with a max dose of 5 mg PO (45 – 60 min before naxitamab infusion) **or** equivalent dose of PO opioids **or**

- In cases where PO administration is not feasible (15 min before naxitamab infusion):
 - Hydromorphone 0.00375 – 0.015 mg/kg IV administration over 2 - 10 min
 - Morphine Sulfate/ Morphine Sodium Chloride 0.025-0.1 mg/kg given IV over 2-10 min
- Corticosteroids (30 min – 2 h prior to naxitamab infusion)
 - All patients at the first infusion in the first cycle must receive:
 - IV methylprednisolone 2 mg/kg with a max dose of 80 mg **or** equivalent corticosteroid dose
 - The same corticosteroid premedication should be given in the following circumstances:
 - At the first infusion in the following cycle if the patients had a CTCAE Grade 3 bronchospasm/anaphylaxis at the last cycle's first infusion
 - At the following infusion if the patient had a Grade 3 bronchospasm/anaphylaxis at the last infusion
 - When infusion related reactions are not sufficiently controlled by the other premedications at the investigator's discretion.
- Antipyretics (30 min before naxitamab infusion)
 - Paracetamol (acetaminophen) 10 mg/kg to maximum 15 mg/kg (max 750 mg total dose) PO or IV
- Antihistamine (30 min before naxitamab infusion)
 - Hydroxyzine 0.5 – 1 mg/kg (max 50 mg) PO/IV, **or**
 - Diphenhydramine 0.5 – 1 mg/kg (max 50 mg) IV **or**
 - Cetirizine <20 kg: 2.5 mg; >20 kg: 5 mg; If > 12y AND > 30 kg: 10 mg PO **or**
 - Loratadine 5 mg for patients 2 – 5 years of age; 10 mg for patient > 5 years of age PO **or**
 - Equivalent according to local SoC
- H₂ antagonist according to local SoC
- Antiemetics (30 min before naxitamab infusion)
 - Ondansetron 5 mg/m² **or**
 - Equivalent according to local SoC

If a patient receives antiemetics prior to IT treatment on Days 2 and 4, additional administration of antiemetics prior to naxitamab infusion will be at the discretion of the investigator
- Anxiolytics, if applicable
 - Lorazepam 0.01 – 0.02 mg/kg (max 1mg) IV pro re nata (PRN) **or**
 - Equivalent according to local SoC

In case of inadequate pain control or hypersensitivity to the above-mentioned pain medications, an alternative strategy to mitigate treatment-induced pain can be introduced at the discretion of the investigator. Ketamine can be a useful alternative to mitigate naxitamab-induced pain⁴⁰. In case of inadequate pain control with opioids, ketamine can be used according to local SoC.

8.4.2 Supportive therapy to be readily available during naxitamab

The following supportive therapies should be readily available at the bedside as pre-prepared treatments when the naxitamab infusion is initiated

- For use at the onset of pain (pre-charged syringes):
 - Hydromorphone 0.00375 – 0.015 mg/kg given IV over 1 – 5 min, **or**
 - Morphine sulfate/ Morphine Sodium Chloride 0.025 – 0.1 mg/kg given IV over 1 – 5 min.
 - Opiate doses may be repeated every 5 min for a total of 4 doses. The low, but frequent intermittent doses are preferred to mitigate the risk of opioid associated hypotension.
 - Additional doses may be ordered and given PRN at the discretion of the treating physician
- PRN:
 - Lorazepam 0.01-0.02 mg/kg PO or IV (max 1 mg) or equivalent according to local SoC
 - H1 receptor blocker according to local SoC (e.g., dexclorfeniramine at 0.15 mg/kg IV (max 5 mg) or diphenhydramine for IV administration)
 - NSAID according to local SoC
 - Methylprednisolone 2 mg/kg IV with a max dose of 80 mg (in case corticosteroid was not given as pre-medication) **or** equivalent corticosteroid dose. If corticosteroid was administered as pre-medication, a dose reduction should be considered at the investigator's discretion
 - Adrenalin (epinephrine) 0.01 mg/kg IV or IM (max 0.5 mg)
 - Selective beta2-adrenergic receptor agonist nebulized administered PRN according to local SoC (e.g., salbutamol < 20 kg: 2.5 mg; >20 kg: 5 mg) for bronchospasm
 - Epinephrine for inhalation PRN for stridor
 - Naloxone IV 1 mcg/kg/doses (to be repeated every 2-3 min until response) for management of potential acute cases of respiratory depression:
 - Saline 0.9% for bolus infusion: 10-20 mL/kg IV according to Section [8.4.5.2](#)
 - Cold and hot pads to be applied locally in any body area ad libitum as part of pain management
 - Oxygen (oxygen mask and humidified oxygen inhalation equipment must be available)

8.4.3 Pre-medication prior to administration of irinotecan

Prevention and management of irinotecan associated diarrhea

Irinotecan associated early and late diarrhea and the risk hereof should be handled according to local SoC. This includes but is not limited to:

- Advise on diet (e.g., to eliminate substances that may contribute to diarrhea)
- Instructions on the use of loperamide
- Instructions on how to prevent diarrhea-induced dehydration
- Instructions on what situations the patient/parent should contact the investigator
- Cephalosporin

- For prevention of irinotecan-associated diarrhea, it is recommended to administer cephalosporin according to SoC (e.g., cefixime 8 mg/kg/day PO once daily or cefpodoxime 10mg/kg/day PO divided into 2 daily doses, maximum dose 400mg/day). Treatment should be started 2 days prior to the first dose of irinotecan and continued until 3 days after the last dose of irinotecan (i.e., a total of 10 days in each cycle)

Pneumocystis prophylaxis

- Patients should receive pneumocystis prophylaxis according to local SoC while on IT treatment

8.4.4 Management of selected IT adverse reactions

8.4.4.1 Management of hematologic toxicities

Patients who experienced hematologic toxicity should receive dose-reduction of IT treatment as described in the following sections at the discretion of the investigator.

Dose-limiting neutropenia

Patients who experience neutropenia (absolute count $<750/\mu\text{L}$) that causes a delay of ≥ 14 days between treatment cycles in the absence of other toxicity requiring dose modification, should have the temozolomide dose reduced by 20% for subsequent cycles (i.e., 80 mg/m²/day see dose reduction nomogram in [Appendix 4](#)). If despite this 20% dose reduction neutropenia (absolute count $<750/\mu\text{L}$) recurs, causing a delay of ≥ 14 days between treatment cycles, reduce the irinotecan dose by 20% (i.e., irinotecan dose 40.0 mg/m²/day) and temozolomide dose by additional 20% (i.e., 60 mg/m²/day see dose reduction nomogram in [Appendix 5](#)) for subsequent cycles. For neutropenia requiring discontinuation of IT (please refer to Section [7.12](#)).

Dose-limiting thrombocytopenia

For patients who experience thrombocytopenia ($<75,000/\mu\text{L}$) that causes a delay of ≥ 14 days between treatment cycles with or without other hematologic toxicities, the dose of temozolomide should be reduced by 20% for subsequent cycles (i.e., 80 mg/m²/day see dose reduction nomogram in [Appendix 4](#)). If despite this 20% dose reduction, thrombocytopenia ($<75,000/\mu\text{L}$) recurs causing a delay of ≥ 14 days between treatment cycles, reduce the irinotecan dose by 20% (i.e., irinotecan dose 40.0 mg/m²/day) and temozolomide dose by additional 20% (i.e., 60 mg/m²/day see dose reduction nomogram in [Appendix 5](#)) for subsequent cycles. For thrombocytopenia requiring discontinuation of IT (please refer to Section [7.12](#)).

Delayed recovery of platelets, neutrophils, hepatic and/or renal laboratory parameters

Patients who do not meet laboratory criteria to start the next treatment cycle (see eligibility criteria Section [7.11.2](#)) within 21 days after the planned subsequent cycle start date (i.e., there is a ≥ 3 -week delay in start of next cycle) must be discontinued from IT.

8.4.4.2 Management of non-hematologic toxicities

Patients who have experienced non-hematologic toxicity should receive dose-reduction of IT treatment as described in the following sections at the discretion of the investigator.

Dose modification for diarrhea

See Section [8.4.3](#) for patient/family instructions for supportive care measures for patients who develop therapy-associated diarrhea.

- If \geq CTCAE Grade 3 therapy-associated diarrhea is experienced by a patient despite maximal use of anti-diarrheal medications and appropriate use of prophylactic antibiotics, the dose of irinotecan should be reduced by 20% for subsequent cycles (i.e., irinotecan dose $40.0 \text{ mg/m}^2/\text{day}$)
- For treatment related diarrhea requiring discontinuation of IT (please refer to Section [7.12](#))

An IT cycle should not be initiated until treatment-related diarrhea is recovered to \leq CTCAE grade 1.

Dose modifications for nausea and vomiting

- For patients with \geq CTCAE Grade 3 regimen-related nausea and/or vomiting adjustments in the anti-emetic regimen should be made during the next cycle of therapy
- If \geq CTCAE Grade 3 regimen-related nausea and/or vomiting recurs despite optimized anti-emetic usage, doses of IT should be reduced by 20% for subsequent cycles (ie, irinotecan dose $40 \text{ mg/m}^2/\text{day}$; for temozolomide see dose reduction nomogram in [Appendix 4](#))
- For \geq CTCAE Grade 3 regimen related nausea and/or vomiting requiring discontinuation of IT (please refer to Section [7.12](#))

Dose modifications for dehydration

- If dehydration is related to diarrhea or nausea/vomiting, the guidance in the preceding section should be followed
- If regimen-related \geq CTCAE Grade 3 dehydration persists for > 3 days in the absence of significant diarrhea or nausea/vomiting, doses of IT should be reduced by 20% for subsequent cycles (i.e., irinotecan dose $40 \text{ mg/m}^2/\text{day}$; for temozolomide see dose reduction nomogram in [Appendix 4](#))
- For recurrent \geq CTCAE Grade 3 regimen-related dehydration requiring discontinuation of IT, please refer to Section [7.12](#))

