7.12 Premature Discontinuation of Treatment

General discontinuation criteria

A patient should be discontinued from treatment with all IMPs if any of the following situations occur:

1. Grade 4 anaphylaxis related to naxitamab
2. Grade 3 anaphylaxis related to naxitamab not responding to medical intervention at the discretion of the investigator
3. Grade 4 sensory neuropathy or Grade 3 sensory neuropathy that interferes with daily activities for more than 2 weeks at the discretion of the investigator
4. CTCAE Grade 3 pain unresponsive to maximum supportive measures at the discretion of the investigator
5. Grade 4 bronchospasm
6. Grade 3 bronchospasm not responding to medical intervention at the discretion of the investigator
7. Posterior reversible encephalopathy syndrome (PRES)
8. The investigator judges it necessary for medical reasons/non-compliance
9. The patient receives prohibited therapy and/or procedures during the trial, see Section [8.4.8](#)
10. Pregnancy
11. Patient/legal guardian withdraw consent to treatment
12. PD

Discontinuation criteria for IT

A patient should be discontinued from IT treatment if any of the following situations occur:

1. If the patient experiences neutropenia that causes a delay \geq 14 days after the first dose reduction by 20% of irinotecan and the second dose reduction by 20% of temozolomide
2. If the patient experiences thrombocytopenia that causes a delay \geq 14 days after the first dose reduction by 20% of irinotecan and the second dose reduction by 20% of temozolomide
3. If the patient does not meet the criteria to start the next cycle within 21 days after the planned subsequent cycle start date
4. Recurrence of \geq Grade 3 diarrhea despite maximal use of anti-diarrheals, prophylactic antibiotics, and a dose reductions of irinotecan of 20%
5. Recurrence of \geq Grade 3 regimen-related nausea and/or vomiting despite optimization of anti-emetic drugs and a dose reduction of IT by 20%
6. If \geq Grade 3 regimen-related dehydration recurs and persists for >3 days despite a dose reduction of IT by 20%

Discontinuation criteria for GM-CSF

A patient should be discontinued from GM-CSF treatment if any of the following situations occur:

1. Injection site reactions \geq CTCAE Grade 3
2. Allergic reactions (including anaphylactic reactions) \geq CTCAE Grade 3

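### Section 8.4.4.2: the doses named for the 20% IT cut after prolonged isolated dehydration are no cut at temozolomide/irinotecan 80/40 and point to a higher temozolomide table at 60/40

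*Combined protocol and SAP*

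**What the plan says.** Doses below are written temozolomide/irinotecan in mg/m²/day. Treatment starts at 100/50 (sections 8.1.2.1 and 8.1.2.2).

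- **Dehydration, section 8.4.4.2.** When Grade 3 or higher regimen-related dehydration lasts more than 3 days, "in the absence of significant diarrhea or nausea/vomiting, doses of IT should be reduced by 20% for subsequent cycles". The bracket that follows gives irinotecan 40 and, "for temozolomide see dose reduction nomogram in" Appendix 4, the 80 mg/m²/day table. No condition is placed on the patient's current dose.
- **Nausea/vomiting, same section.** If the Grade 3 or higher event "recurs despite optimized anti-emetic usage, doses of IT should be reduced by 20% for subsequent cycles", the same two doses are named.
- **Diarrhea, same section.** After Grade 3 or higher diarrhea despite maximal supportive treatment, "the dose of irinotecan should be reduced by 20% for subsequent cycles", to 40. Temozolomide is not touched.
- **Neutropenia and thrombocytopenia, section 8.4.4.1.** After a delay of at least 14 days, neutropenic patients "should have the temozolomide dose reduced by 20% for subsequent cycles", giving 80; the thrombocytopenia rule is alike. After a second such delay irinotecan goes to 40 "and temozolomide dose by additional 20" percent, giving 60 by Appendix 5.
- **Stopping IT, section 7.12.** Criterion 6 applies if "regimen-related dehydration recurs and persists for >3 days despite a dose reduction of IT by 20" percent. Criterion 5 does the same for nausea/vomiting that recurs after optimized anti-emetics and a 20% IT cut.
- **Discretion.** Section 8.4.4.2 provides "dose-reduction of IT treatment as described in the following sections at the discretion of the investigator".

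**The concern.** The dehydration rule has two parts: an instruction to reduce by 20%, and a statement of the doses that result. They agree for a patient on full dose. The other rules in section 8.4.4 lower one or both drugs for later cycles, so a patient can reach a first dehydration episode on less than full dose. The instruction then says to reduce, while the named doses may say no change or more temozolomide.

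What is at stake is consistent dosing of a child with severe toxicity. Two sites could treat the same patient differently, each with support in the text. The efficacy analysis is not at stake.

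**Working it through.** **Inputs.** Starting doses 100/50 (8.1.2.1, 8.1.2.2). Named result 80/40 (8.4.4.2 with Appendix 4). Hematologic steps to 80/50 and then 60/40 (8.4.4.1). Diarrhea step on irinotecan to 40 (8.4.4.2).

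**Step 1: reproduce the plan's figures.** 100 × 0.8 = 80 and 50 × 0.8 = 40. The named doses are a 20% cut from the starting doses.

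**Step 2: list the states that section 8.4.4 can create before any dehydration cut, and apply 80/40 to each.** Change = named dose / current dose − 1.

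| Current state | How reached | Temozolomide | Irinotecan |
|---|---|---|---|
| 100/50 | start | 80/100 − 1 = −20% | 40/50 − 1 = −20% |
| 80/50 | first hematologic step | 80/80 − 1 = 0% | 40/50 − 1 = −20% |
| 100/40 | diarrhea | 80/100 − 1 = −20% | 40/40 − 1 = 0% |
| 80/40 | first hematologic step plus diarrhea, or the vomiting cut | 80/80 − 1 = 0% | 40/40 − 1 = 0% |
| 60/40 | second hematologic step | 80/60 − 1 = +33% | 40/40 − 1 = 0% |

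At 80/50 and 100/40 the named doses still lower the regimen, through one drug. At 80/40 they change nothing. At 60/40 they point to the higher temozolomide table.

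**Step 3: the 60/40 case in milligrams.** Appendices 4 and 5 both use a child of 0.66 m² as an example. Appendix 4: 0.66 × 80 = 52.8, given as 55 mg. Appendix 5: 0.66 × 60 = 39.6, given as 40 mg. The difference is 15 mg/day (55/40 − 1 = +37.5%), or 15 × 5 = 75 mg over a 5-day course. Below 0.5 m² the figures are 2.6 and 2.0 mg/kg (2.6/2.0 − 1 = +30%).

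**Step 4: does another clause settle these two states?**

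- *Recurrent vomiting at 80/40 or 60/40:* yes. Both drugs are already reduced by at least 20%, so criterion 5 of section 7.12 stops IT.
- *First isolated dehydration at 80/40 or 60/40:* no. Criterion 6 requires dehydration that has come back after an IT cut.
- *Appendices 4 and 5:* in part. Appendix 4 permits a second temozolomide step to 60 if the toxicity recurs, and Appendix 5 directs that step for temozolomide toxicities that recur after the first cut. A new toxicity of a different kind is not clearly included. Section 8.4.4.2 does not cite Appendix 5, and neither appendix gives an irinotecan dose.

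**Step 5: what a 20% cut would be at 80/40.** Taken from the current dose: 80 × 0.8 = 64 and 40 × 0.8 = 32. Taken as 20% of the starting dose, as the hematologic ladder 100, 80, 60 does: 80 − 20 = 60 and 40 − 10 = 30. The protocol defines a temozolomide level of 60 but no irinotecan level below 40.

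**The case against.** The case for leaving the text alone has several parts.

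- **The trigger is narrow.** The dehydration must be regimen-related, severe, prolonged and not explained by diarrhea or vomiting; otherwise the preceding rules apply. The patient must also already be at 80/40 or 60/40. Reaching 60/40 takes two delays of at least 14 days, each ending before the 21-day limit at which IT stops. This stands, and the point is a small one.
- **Appendix 5 already supplies the step from 80 to 60.** It refers to section 8.4.4 as a whole and speaks of toxicities in the plural. This largely stands for temozolomide: the intended next level is visible. It does not fully close the gap, because the wording is about recurrence and the dehydration rule points to Appendix 4.
- **There is a way out.** Reductions are discretionary, and section 7.2.1 with Appendix 2 offers naxitamab + GM-CSF alone when IT is stopped for unacceptable toxicity. True, but discretion over reductions as described does not help where the described dose is the current one.
- **80/40 may be meant as a fixed reduced level.** Every irinotecan cut in 8.4.4 ends at 40, so a floor is plausible. On that reading the moves from 80/50 and 100/40 are right. But 80 is not the temozolomide floor, because section 8.4.4.1 goes to 60, and no floor is stated for irinotecan.

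Two stronger readings are tempting. A reader might infer from the table that the rule fails in four of five states. The documents do not support that: in two of the four it still lowers one drug, and nothing says how often each state occurs. A reader might also infer that the protocol orders a temozolomide increase at 60/40. It does not: the governing verb is to reduce, the table cited is one for reduced dosing, and section 8.4.4.1 sets 60/40 for subsequent cycles.

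**Conclusion.** The point holds for one situation: a first episode of isolated Grade 3 or higher dehydration lasting more than 3 days in a patient already at 80/40 or 60/40 for another toxicity. At 80/40 the named doses are a 0% cut of both drugs. At 60/40 they name a temozolomide level 33% higher with irinotecan unchanged, which contradicts both the instruction to reduce and the hematologic rule. Recurrent vomiting in these states is handled by stopping IT.

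This rests on reading the named doses literally and on earlier reductions carrying forward, as section 8.4.4 says they do. The frequency of these states is not in the documents, but the combination must be rare, and an actual increase is unlikely. ORR, sample size and alpha are unaffected. It is a minor dosing-text correction, worth making because it concerns severe toxicity in children and costs little.

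**What to change.** Add to section 8.4.4.2:

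> *The named doses apply to a drug still at its starting dose. If temozolomide is already at 80 mg/m²/day, reduce to 60 mg/m²/day (Appendix 5). A per-m² dose of irinotecan or temozolomide already reduced for any toxicity is not raised by these rules.*

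The last sentence is written per m² because section 9.3.2 recalculates BSA before each cycle, so a growing child's milligram dose may properly rise. A no-raise sentence alone would leave 80/40 unresolved, which is why the step to 60 is stated.

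Two clinical decisions remain for the sponsor's clinical team: whether 40 mg/m²/day is the lowest irinotecan dose, and what applies at 60/40. No new stopping rule is proposed here.

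The cost is a small wording amendment, which needs the usual submission and approval under section 14.3. It needs no new data, visits or patients.
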